## Research Design and Methods

Describe in detail the methods and procedures that will be used to accomplish the objectives and specific aims of the project. Discuss the alternative methods that are available and justify the use of the method proposed in the study. Justify the scientific validity of the methodological approach (biomedical, social, or environmental) as an investigation tool to achieve the specific aims. Discuss the limitations and difficulties of the proposed procedures and sufficiently justify the use of them. Discuss the ethical issues related to biomedical and social research for employing special procedures, such as invasive procedures in sick children, use of isotopes or any other hazardous materials, or social questionnaires relating to individual privacy. Point out safety procedures to be observed for protection of individuals during any situations or materials that may be injurious to human health. The methodology section should be sufficiently descriptive to allow the reviewers to make valid and unambiguous assessment of the project. (DO NOT EXCEED TEN PAGES. USE CONTINUATION SHEETS).

### Study Design

A rapid survey comprising holding focus group discussions with women in the villages and interviewing key informants will precede the main study. The main study will be a randomized controlled trial of the effect of adding stimulation to the treatment of malnourished children in feeding centers. Narsingdi thana which is close to Dhaka was recently visited by the investigators and was selected for the study. There are on average 8-10 moderately and severely malnourished children in each feeding center at any time. Twenty selected centers will be randomly assigned to treatment or control groups. (It is not considered ethical to randomize individually within each center). The intervention will run for one year and the outcome measures will be assessed in mothers and children both before and after the study

In addition to the treatment trial, a cohort of matched adequately nourished children will be studied to compare with the malnourished groups. They will come from the same villages served by the intervened centers and will fulfil the same criteria for age, area of residence, and socio-economic background to the intervened children. This comparison will enable us to determine the initial behavioral and psychomotor deficits in the malnourished groups and assess whether the children return to levels normal for their community following intervention.

Recognizing that the children are clustered into feeding centers or villages we will use multilevel modelling in the analyses to enable us to analyze data at the individual child level as well as examine the variance by feeding center and treatment group.

### Survey of Child Rearing Practices

Two focus groups with approximately six mothers of children under 5 years of age will be held in 3 control villages and 3 intervention villages. Mothers of malnourished children attending the feeding centers will not be involved.

Each focus group will have a leader and a recorder. The leaders will be [name], [name] and the senior psychologist. Information will be sought on all activities mothers do with their babies, their attitude towards play and child development, knowledge of child development and any games, songs and nursery rhymes, their aspirations for their children and who makes decisions in the family about child care and education.

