## Measurements

The Drs [name] and [name] will do the piloting and quality control of all measurements.

**Developmental level:** The infants will be assessed on the Bayley Scales of Mental Development at the beginning and end of the study. We have used these scales before in Bangladesh and good interobserver reliability was attained. The assessments will be done by one of two trained female psychologists who are unaware of the children's group assignment. Care will be taken to keep the testers blind to the child's group and the testing will not be done in the feeding centers.

**Behavior:** The children's behavior during the tests will be rated by the testers on five 9 point scales: the amount of vocalisation, co-operation with the test procedure, activity level, emotional tone and response to examiner. These scales have also been used before in Bangladesh and are modified from those of Bayley and Wolke et alxxi.

**Temperament:** At the end of the study the mothers will be given a questionnaire by the psychologists concerning their child's temperament. There is no standardised test for Bangladeshi children. We will therefore pilot an instrument developed by Mary Rothbartxxii and one being developed by Theodore Wachs from Purdue University for use in Jamaica and Peru and combine and modify the instruments where necessary. The following behaviors will be investigated: activity level, positive emotionality (smiling/laughing), negative emotionality (fussing/crying), social approach (response to strange adults), object fear (fear of new objects), attention/orientation, manageability (response to frustration/ co-operativeness), soothability (reduction of distress in response to soothing). These behaviors are well recognised components of temperamentxxiii.

**Anthropometry:** All children will have their weights, lengths, head and mid upper arm circumferences measured using standard techniques on enrolment and every 3 months by the research assistant.

**Socio-economic background and stimulation in the home:** All homes will be visited at the beginning of the study and information will be sought on the families' wealth, standard of housing, family structure and parental characteristics. The stimulation in the home will be assessed using a modified version of the Betty Caldwell home inventoryxxiv, which was modified for Bangladesh in a previous study by this research group.

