**Child rearing practices:** The mothers' knowledge of child development and child rearing practices will be assessed at the beginning and end of the study by the psychologist.

**Hb Measurement:** As suggested by one of the reviewers, we will consider testing the children for their Hb level provided funds are available.

**Quality Control of Measurements:** Before the study begins, and after training the measurers, inter-observer reliabilities will be assessed for all measures. Values of over  $r > 0.9$  are expected for all measures and training will continue until this standard is attained. Five to 10 percent of all tests throughout the study will be observed and independently scored by an observer. Test-re-test reliabilities

Principal Investigator: Last, first, middle [name]

will also be assessed at the beginning of the study for the temperament scales and Bayley test in 20 subjects and values  $>0.7$  are expected.

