### **Personnel**

PI and Co-PI will supervise the overall activities of the project. They will play the leading role in implementing the research in the field, they will pilot and train the appropriate personnel in all measurements, plan data entry, conduct analyses and write reports.

Co-PI is working at another institution and will give 35% of his time for this project.

The two psychologists will test 300 children and interview the mothers at the beginning and end of the study.

For the intervention group, we need one play leader at each intervention center making a total of 10.

For the control group health workers will arrange for the testing of the children and keep trace of their whereabouts. Therefore, one health worker can cover 2-3 feeding centers making a total of 4 health workers.

To make frequent visits to the project sites, which are situated outside the city in the rural area, we require a vehicle and a driver.

To supervise the work of the play leaders and help in record keeping, we need a research assistant.

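### Blinding of the developmental testers is promised but put at serious risk by their other duties, and growth is measured by the play leaders' supervisor

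*Protocol*

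**What the plan says.** All references are to the psychosocial stimulation study in the Protocol.

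- **Promise of blinding.** Measurements, on developmental level: "The assessments will be done by one of two trained female psychologists who are unaware" of group assignment. Two safeguards are named: general care, and testing away from the feeding centers. The same testers rate behavior on five 9-point scales.
- **Maternal interviews.** Measurements, on the mothers: knowledge of child development and "child rearing practices will be assessed at the beginning and end of the study by the psychologist". Budget Justifications, Personnel: "The two psychologists will test 300 children and interview the mothers at the beginning and end of the study". The psychologists also give mothers the temperament questionnaire at the end.
- **Focus groups.** Survey of Child Rearing Practices: two groups of mothers "will be held in 3 control villages and 3 intervention villages", led by two named people "and the senior psychologist".
- **Growth.** Objective 2 lists growth in height and weight for height among the comparisons of the randomised groups. Measurements, on anthropometry: taken "on enrolment and every 3 months by the research assistant". Budget Justifications, Personnel: "To supervise the work of the play leaders and help in record keeping, we need a research assistant".

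**The concern.** The Bayley score and, still more, the behavior ratings depend on the judgement of the person scoring. A tester who knows the arm may score intervention children more kindly without meaning to. Neither a larger sample nor the multilevel model removes that kind of error. The protocol recognises this and promises blind testers, but then gives those testers tasks that are likely to show them the arm. Length in children of this age depends on technique, and the person measuring it oversees delivery of the intervention.

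**Working it through.** There is no stated figure to reproduce. The check sets the staff assignments side by side, with simple arithmetic on posts, timing and load.

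**1. Who the psychologists are.** The Detailed Budget has 2 psychologist posts at US$455 a month: 2 × 455 × 12 = 10,920, which matches the entry for each of years 1 and 2. Both are therefore paid from the first month, when the Time Schedule places the survey. No third psychologist is budgeted, and none of the five key personnel is listed as one; the nearest is a professor of child development. Neither budgeted post is called senior. That the senior psychologist is a tester is therefore a likely inference and not a stated fact.

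**2. What the closing interview reveals.** The Intervention section has mothers attend weekly for a year, learning how to play with, talk to and teach their children. The interview asks about child-rearing practice and knowledge of child development. A mother's answers at the end are thus likely to show whether she attended. Baseline interviews should not do this, since they come before the teaching.

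**3. How far one disclosure reaches.** Allocation is by center, with the first 10 eligible children measured in each (Samples). Enrolment runs over 5 months and post-testing over another 5, so a center's children can be expected to come for testing at different times. Either psychologist may test any child. Suppose every child is tested before his or her own mother is interviewed. The first revealing interview still discloses the arm for up to 10 − 1 = 9 later children of that center. Fixing the order within a family is therefore not enough.

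**4. Focus-group route.** To choose three villages of each kind, someone must already know the allocation. By the Time Schedule the survey is in months 1–2, baseline testing begins after 2 + 4 = 6 months, and post-testing after 2 + 4 + 5 + 7 = 18 months. The route covers 6 villages, against 20 centers. It is real but weaker than the interviews.

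**5. Growth.** The budget has one research assistant: 6,272 / 224 = 28 months, the whole project. Play leaders exist only at the 10 intervention centers. The one person who measures growth in both arms therefore knows which centers are intervention centers.

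**6. Load under a split by center.** At present: 300 / 2 = 150 tests per psychologist, or 150 / 5 = 30 a month in the post-test period. Under the split, each psychologist tests 5 of the 10 centers in each arm: 5 × 10 × 2 = 100 malnourished children. Half of the 100 comparison children, kept with the center of their matched child, adds 50, giving 150 again. Interviews divide in the same way. The testing load does not change.

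**The case against.** The strongest reply is that none of this shows a tester actually learning the arm. The protocol promises care, tests in a rented house in Narsingdi town, expects inter-observer reliability above 0.9, and has 5 to 10 percent of tests independently scored throughout. The order of test and interview is simply unstated, and visit order is normal field-manual content. The focus groups are early and few, and "Mothers of malnourished children attending the feeding centers will not be involved", so they expose no study child. Blinding is claimed only for the developmental testers, growth is not the outcome behind the sample size, and anthropometry uses standard techniques.

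Much of this stands. A reader might infer that the staffing does unblind the assessment; the documents support only a serious risk. A reader might also call the growth arrangement a contradiction; it is an unprotected outcome, because no blinding was promised there. The focus-group route needs an inference about who the senior psychologist is, and reveals villages, not individual children.

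Two parts of the reply do not hold. Agreement between two observers does not detect a bias they share, and the observers are not said to be blind. And the interview problem is more than a missing sequence: the protocol positively assigns testing and interviewing to the same two people under center allocation, and step 3 shows that a within-family order would not cure it.

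**Conclusion.** The concern holds as a risk to blinding that should be reduced before the study starts. The main route is the end-of-study maternal interview by the testers, and the lesser one is the focus groups. Growth is a separate weakness: its measurer knows the arm and supervises the intervention staff.

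The size of any bias cannot be computed from the documents. One could assume a tester leniency of 1 to 2 DQ points and set it against the 6-point target (1/6 = 17%, 2/6 = 33%), but nothing in the protocol supports that leniency, so these percentages are not a finding. Nor do the documents show that growth results would be biased toward the intervention. The conclusion rests on two assumptions: that mothers' closing answers tend to reveal attendance, and, for the focus-group route only, that the senior psychologist is one of the two testers.

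**What to change.** 1. **Focus groups.** Hold them before centers are randomised, or have only the two other named leaders run them. The survey serves to design the intervention, and arm labels are not needed for that.
2. **End-of-study testing and interviews.** Split by center within each arm. Each psychologist tests the children of half the centers and interviews only mothers from the other half, with the temperament questionnaire counted as part of the interview. Complete and seal each child's Bayley and behavior ratings before that mother's interview. Swapping interviewers child by child would not work, because the interviewer would then test other children from a center whose arm she had learned.
3. **Growth.** Where existing staff allow, have the testing psychologist take baseline and final length and weight at the test house, before any interview, for the comparison between arms. Keep the research assistant's 3-monthly values as supporting data. If this is not feasible, state that growth was measured unblinded. The four health workers are no substitute, since they serve the control arm only.

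The cost is extra scheduling and a small added measuring load, with no new post. The change lowers the risk without guaranteeing blinding, since a mother may still talk during the test.

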## Treatment Trial

### Samples

The study will be conducted in BINP nutrition centers in the Narsingdi Thana. Narsingdi which is situated near Dhaka and has a total population of 353,275 out of whom, there are 21,090 children below the age of 2 years. About 2229 of these children require nutritional supplementation and are enrolled in the BINP community nutrition centers. Narsingdi thana comprises 14 unions with 17-29 feeding centers in each union making a total of 326 feeding centers. Only six of these unions are accessible to Dhaka. For ethical reasons randomization into intervention and control will be by centers and not within each center. Twenty feeding centers from the two unions most accessible to Dhaka, will be selected to participate in the study. Only centers expected to enrol at least 10 children in the five month enrolment period will be selected. The sampling will be in two steps. In the first step, centers that are so close to each other that there is a high probability of the mothers or staff mixing socially, will be formed into clusters. One center from each cluster will then be randomly selected for further sampling. The first stage should prevent any spill over between treatment groups. In the second step 10 centers will be randomly selected for the intervention group and 10 for the control group, from the two unions.

A sample of 84 in each group will be sufficient to detect a difference of 6 developmental quotient (DQ) points between the groups with a power of 90% at the 5% level of significance. Assuming a loss of 16% we need 100 children in each group.

The study will have 3 groups making a total of 300 children who will have all measurements. However, because we want to assess the feasibility of incorporating this programme into a service model we will enrol into the intervention all children who present at the centers and fit the enrolment criteria during the enrolment period. The extra children will not have the measurements but enrolling all available children into the intervention will enable us to determine any problem with implementation at a service level.

**Treatment group:** The first 10 children referred to each intervention feeding center after the beginning of the study, and fulfil the selection criteria will be enrolled making a total of 100. However, all the children attending the intervention centers will have play opportunities.

**Control group:** The first 10 children referred to each control feeding center after the beginning of the study and fulfil the selection criteria will be enrolled making a total of 100.

**Inclusion criteria:** weights for age  $<-2sd$ , aged between 6 and 24 months, mothers agree to participate in the study and intend to stay in the area for the next year.

**Exclusion criteria:** twins and disabled children will be included in the intervention for ethical and demonstration purposes but will not be part of the evaluated sample.

**Comparison group:** The child living nearest to every treated malnourished child with weight for age  $>-1sd$ , of the same age ( $\pm$  one month) and sex, maternal education and standard of housing will be enrolled making a total of 100.

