## Data Analysis

Describe plans for data analysis. Indicate whether data will be analyzed by the investigators themselves or by other professionals. Specify what statistical softwares packages will be used and if the study is blinded, when the code will be opened. For clinical trials, indicate if interim data analysis will be required to monitor further progress of the study. (TYPE WITHIN THE PROVIDED SPACE).

The qualitative data will be analysed using the framework procedures identified by Ritchie and Spencerxxv including indexing, charting, mapping and interpretation.

For the quantitative data, all test records will be checked by a second person and double entered into the computer. All continuous variables will be examined for normality and transformed if necessary. Initial differences between the randomized malnourished groups will be examined using t-tests or analysis of variance for normally distributed data and chi-squared or Mann-Whitney for non-normal data. To compare initial differences between the adequately nourished and malnourished groups the enrolment data for the two malnourished groups will first be combined. When analyzing behavioral data, age and sex will be controlled if they are significantly related to the outcome variable.

As the sample is clustered into feeding centers, multi-level modelling will be used to examine the treatment effect on the children's development, behavior, and temperament and on the maternal outcomes. For this analysis, we will use the computer package designed by the Institute of Education, Londonxxvi. The model used will have 3 levels, the individual child, the feeding centers and the treatment group. With this model we will be able to control for random variance at each of these levels and to examine whether treatment has different effects in different centers.

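### Center allocation is not stated to be stratified by union, and the planned model has no union term: a valid design with a cheap improvement available

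*Protocol*

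**What the plan says.** The protocol's Samples section gives the unit of allocation: "For ethical reasons randomization into intervention and control will be by centers and not within each center". The source of the units is also stated: "Twenty feeding centers from the two unions most accessible to Dhaka, will be selected to participate in the study".

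Sampling then has two steps. First, centers whose mothers or staff are likely to mix are grouped, and "One center from each cluster will then be randomly selected for further sampling". The stated purpose is to prevent spill-over between arms; the step does nothing to balance unions. Second, "10 centers will be randomly selected for the intervention group and 10 for the control group, from the two unions". Study Design repeats the allocation in brief: "Twenty selected centers will be randomly assigned to treatment or control groups". Neither place mentions strata, pairs or blocks.

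On the analysis side, the Data Analysis section says: "The model used will have 3 levels, the individual child, the feeding centers and the treatment group". Union appears neither as a level nor as a covariate.

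The protocol does not say how many of the 20 centers lie in each union. It gives only the range for the whole thana: "Narsingdi thana comprises 14 unions with 17-29 feeding centers in each union making a total of 326 feeding centers".

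**The concern.** Union is known for every center before allocation and has only two levels, and there are only 20 units to allocate. As described, the plan handles it neither in the randomisation nor in the model. If the two unions differ in anything related to child development, an uneven draw carries part of that difference into the treatment contrast of the trial that is actually run.

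The protocol itself treats area as worth controlling elsewhere: the Objectives and Study Design list area of residence among the matching factors for the adequately nourished children. Those children come only from villages served by intervention centers, while the baseline comparison pools both malnourished arms. A union imbalance between arms would therefore also loosen the area match for the control half of that pool.

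An analysis plan could later add a union term, but it could not restore balance once centers have been allocated. That is why the point belongs to the protocol.

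**Working it through.** **The plan's own figures.** The Samples section says "A sample of 84 in each group will be sufficient to detect a difference of 6 developmental quotient (DQ) points between the groups", with 90% power at the 5% level, and allows for a 16% loss. Inflation: 84 / (1 - 0.16) = 100 per group, as stated. No SD is given. Solving 84 = 2 × (1.960 + 1.282)² × SD² / 6² gives SD ≈ 12.0 (two-sided test assumed). Nothing below changes the sample size.

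**Inputs.** From the protocol: 20 centers, 10 per arm, two unions, 10 evaluated children per center, target 6 DQ points. Assumed, because the protocol does not give them: the number K of the 20 centers that lie in one union (range 5 to 10), and the difference D between unions in mean DQ (illustrated at 3 points).

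**Chance of imbalance.** With 10 of the 20 centers drawn for intervention without regard to union, the number k from a union with K centers is hypergeometric:

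P(k) = C(K, k) × C(20 - K, 10 - k) / C(20, 10), where C(20, 10) = 184,756.

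For K = 10:

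- 5:5: 252² / 184,756 = 34.4%
- 6:4 either way: 2 × 210² / 184,756 = 47.7%
- 7:3 either way: 2 × 120² / 184,756 = 15.6%
- 8:2 or worse: 2.3%

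So 6:4 or worse is 65.6%, and 7:3 or worse is 17.9%. About 48 of the 66 percentage points are the 6:4 split.

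For other values of K, with imbalance measured as the difference between arms in the number of centers from that union:

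| K : 20 - K | difference of 2 or more | difference of 4 or more |
|---|---|---|
| 5:15 | 30% | 3% |
| 6:14 | 63% | 14% |
| 7:13 | 35% | 6% |
| 8:12 | 65% | 17% |
| 9:11 | 37% | 7% |
| 10:10 | 66% | 18% |

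**Effect on the contrast.** With equal numbers of children per center, the arms differ in their share of a union by (2k - K)/10, so the contrast shifts by (2k - K)/10 × D. For K = 10 and D = 3:

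- 6:4: 0.2 × 3 = 0.6 points
- 7:3: 0.4 × 3 = 1.2 points
- 8:2: 0.6 × 3 = 1.8 points

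The average absolute shift over all draws is about 0.17 × 3 = 0.5 points.

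**Seen as precision.** For K = 10 the SD of the share difference is 0.229, so D = 3 adds a component with SD 0.229 × 3 = 0.69 points. The stated design implies a standard error of 6 / (1.960 + 1.282) = 1.85. Combining them gives √(1.85² + 0.69²) ≈ 1.97, and power falls from 90% to roughly 86%. This is a rough guide: it rests on the assumed D, K and two-sided test, and it leaves out all other center-level variance.

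**With allocation within union.** If K is even, each union divides equally. If K is odd, the arms differ by one center of each union, in opposite directions, so 10:10 is kept and the shift at D = 3 is at most 0.1 × 3 = 0.3 points.

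**The case against.** The case against is substantial, and most of it stands.

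- *The design is valid.* Allocating 20 centers 10:10 at random contradicts nothing and gives an estimate that is unbiased over draws. A union effect is part of the variation between centers, and the planned model carries center as a level. This stands. A reader might infer that the treatment estimate is biased; the documents do not support that. What can occur is chance imbalance in the realised draw, and some loss of precision.
- *A single pooled draw is inferred.* It is the natural reading, but the wording does not strictly exclude drawing within each union. This stands, and is a reason to clarify the sentence.
- *Nothing shows that union is prognostic.* Both unions lie in one thana and were picked by the same accessibility criterion, and Facilities Available describes the centers as organised and supervised in common. This stands. The matching on area shows that the investigators care about locality, not that these two unions differ.
- *Serious imbalance is not likely.* A reader might take the 66% together with a 6-point union difference at 7:3 (0.4 × 6 = 2.4 points, 40% of the target) and infer a probable large distortion. That joins the probability of a mild split to the consequence of a less common one, and assumes a union gap as large as the whole target effect. The documents support neither step.
- *Baseline data would reveal a problem.* Development, home stimulation, wealth and housing are measured at enrolment, and initial differences between the randomised groups are to be examined. This is partly right: a material imbalance would be visible, but Data Analysis does not commit to adjusting for it.
- *Model terms belong to the analysis plan.* This is fair for the covariate, but not for the allocation, which the protocol describes itself.

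**Conclusion.** The point holds as a low-severity design improvement. The protocol states no stratification by union, and its model omits union, so a factor known before allocation is handled in neither place. Some imbalance is more likely than not when the split between unions is even-numbered (63-66% for K = 6, 8 or 10), but it is usually mild. A between-arm difference of four or more centers has probability 3-18% over assumed splits of 5:15 to 10:10. The shift of 0.6 points at 6:4 and 1.2 at 7:3 depends wholly on an assumed 3-point union difference. It would not invalidate the trial or alter the planned numbers.

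**What to change.** In the second sampling step of the Samples section, state that once one center has been drawn from each social cluster, centers are randomised separately within each union, as equally as the number allows. With 10 centers per union this means 5 and 5. With odd numbers, the extra center goes to opposite arms in the two unions, decided at random, so that 10:10 is kept. State also how many of the 20 centers each union supplies. In Data Analysis, add union as a fixed factor in the multilevel model. If allocation within union is already intended, saying so is enough for the design part.

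The cost is one sentence in each section and about one of 18 center-level degrees of freedom (20 centers less two arms), leaving 17. No extra centers, children or staff are needed. If the unions do not differ, the gain is small, and the lost degree of freedom is the only price.

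### The 90% power for 6 DQ points shows no allowance for the randomisation of 20 feeding centers; if the SD is 12, as the figure suggests, unadjusted power falls below 90% at any positive ICC

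*Protocol*

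**What the plan says.** The sample-size statement is in the Samples section under Treatment Trial: "A sample of 84 in each group will be sufficient to detect a difference of 6 developmental quotient (DQ) points between the groups". Power is put at 90% and the significance level at 5%. The only inflation is for attrition: "Assuming a loss of 16% we need 100 children in each group".

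The unit of allocation is the center. Study Design says "Twenty selected centers will be randomly assigned to treatment or control groups", and Samples repeats it: "For ethical reasons randomization into intervention and control will be by centers and not within each center". There are 10 centers per arm, and the first 10 eligible children at each are enrolled for measurement.

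The Data Analysis section acknowledges the consequence for the test: "As the sample is clustered into feeding centers, multi-level modelling will be used". Study Design says much the same.

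Neither the sample-size paragraph nor any other part of this protocol states an SD for the developmental quotient, an ICC, a design effect or an adjustment for the number of centers.

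**The concern.** When whole centers are allocated, children from the same center share a play leader, group sessions and a village, so their scores may be correlated. The treatment effect is then judged against variation between centers, and 84 children in 10 centers carry less information than 84 independent children. The protocol builds this into its analysis but shows nothing of it in its sample size. The power claim and the planned test therefore appear to describe different designs.

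This is the only power statement for the stimulation trial, whose long-term aim is to spread the program to all centers. If the true power for 6 points is well below 90%, a null result read against the stated figure could be taken as stronger evidence against a 6-point effect than the design can supply.

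**Working it through.** **Inputs from the protocol.** 84 analysed per group; difference 6 DQ points; power 90%; level 5%; loss 16%; 10 centers per arm; 10 children enrolled per center, so 10 × 0.84 = 8.4 analysed.

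**Inputs assumed here.** Two-sided test (sidedness is not stated); SD back-solved; ICC 0.01 to 0.10; for the second set of power figures, a t test with 2 × 10 − 2 = 18 df.

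**Step 1: the plan's own figure.** For independent children, n per group = 2(1.960 + 1.282)² SD² / 6².
- Setting n = 84 gives SD = 6 / (3.242 × √(2/84)) = 11.996.
- Forward with SD 12, n = 84.06, and power at 84 is 0.900.
- A one-sided test would need SD 13.3.
- Attrition: 84 / 0.84 = 100, which agrees with the protocol.

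So 84 is what the formula returns with a round SD of 12 and a design effect of 1. This does not prove that no design effect was used, because the SD was solved on that premise. By normal approximation, 84 also gives 90% power with SD 11.2 at ICC 0.02, SD 10.25 at ICC 0.05, or SD 9.1 at ICC 0.10.

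**Step 2: power for the design as described, taking SD 12.**
- Design effect DE = 1 + (8.4 − 1) × ICC = 1 + 7.4 × ICC.
- Standard error of the difference SE = 12 × √(2 × DE / 84).
- Power (normal) = Φ(6/SE − 1.960).
- Power (18 df): noncentral t with noncentrality 6/SE and critical value 2.101.
- Difference detectable with 90% power: 3.242 × SE (normal), or (2.101 + 1.330) × SE (18 df).

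| Assumed ICC | DE | SE | Power, normal | Power, 18 df | Detectable, normal | Detectable, 18 df |
|---|---|---|---|---|---|---|
| 0 | 1.00 | 1.85 | 90% | 86.5% | 6.0 | 6.4 |
| 0.01 | 1.07 | 1.92 | 88% | 84% | 6.2 | 6.6 |
| 0.02 | 1.15 | 1.98 | 86% | 82% | 6.4 | 6.8 |
| 0.05 | 1.37 | 2.17 | 79% | 74.5% | 7.0 | 7.4 |
| 0.10 | 1.74 | 2.44 | 69% | 64% | 7.9 | 8.4 |

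Example at ICC 0.05: DE = 1 + 7.4 × 0.05 = 1.37; SE = 12 × √(2.74/84) = 2.17; 6/2.17 = 2.77; Φ(2.77 − 1.96) = 0.79.

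The ICC 0 row shows that the 18-df test alone costs about 3.5 percentage points. The rest of the shortfall comes from the ICC.

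**Step 3: effect of baseline adjustment.** If the baseline and final Bayley scores correlate at 0.5 (assumed) and adjustment multiplies the variance by 1 − 0.5² = 0.75 at both levels, power at ICC 0.02, 0.05 and 0.10 is 94%, 89% and 81% (normal), or 91%, 86% and about 77% (18 df).

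**The case against.** The strongest objection is that the SD is not in the document. A reader might infer that 84 can only have come from the independent-children formula, and hence that the trial certainly lacks its stated power. The documents do not support that: Step 1 shows that smaller SDs with a design effect give the same 84. Nothing in the text points to such a calculation, and a round 12 makes the simpler reading more plausible, but it remains an inference. This limits the claim to two parts: no allowance is shown, and the power is lower if the SD is 12.

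Second, the 18-df test is a choice made in this check. The protocol specifies multilevel modelling without a df rule. With 20 centers 18 df is defensible, but it is an assumption, so both sets of figures are shown.

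Third, the Bayley scales are given at the beginning and end of the study, and adjusting for the first score could recover much of the loss (Step 3). But the sample-size statement does not rely on this, and the Data Analysis section does not specify baseline Bayley adjustment for the treatment effect. It tempers the size of the shortfall without supporting the stated figure.

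Fourth, the planned multilevel model already accounts for clustering. That is right for the type I error and counts in the protocol's favour. It does not restore power.

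There is no slip in the attrition arithmetic.

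**Conclusion.** The concern holds in this form: the protocol claims 90% power for 6 points from 84 analysed children per group, randomises centers, and shows no SD, ICC or allowance for clustering, so the claim cannot be verified for the design described. On the most plausible reading, SD 12 with no design effect, any positive ICC takes unadjusted power below 90%. At ICCs of 0.02 to 0.10 it is about 86% down to 69% by normal approximation, or 82% down to 64% with 18 df.

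Given SD 12, the direction does not depend on the ICC chosen; only the size does. The figures rest on a back-solved SD, an assumed ICC range, a two-sided test, equal center sizes of 8.4 and no baseline adjustment. The planned analysis is not at fault. What needs correcting is the planning statement.

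**What to change.** Keep the enrolment. In the Samples section:

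- State the SD of the developmental quotient, the ICC or a range for it, and any baseline Bayley correlation relied on.
- Replace the 90% claim with the power for 6 points, and the difference detectable with 90% power, recomputed for 10 centers per arm with about 8.4 analysed children each.
- Say which reference distribution was used.

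If the sponsor has its own SD and ICC, those should be used. If not, the SD of 12, the ICC range of 0.02 to 0.10 and the 18-df test may serve, each labelled as an assumption. If the sponsor did include a design effect, stating it with the SD would settle the point.

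The cost is one rewritten paragraph and, unless the sponsor's own inputs support 90%, a less favourable power statement. It needs no extra children and no change of procedure. For scale, holding 90% power at 6 points without baseline adjustment would take 84.06 × DE / 8.4 centers per arm with SD 12: about 12, 14 or 18 at ICC 0.02, 0.05 or 0.10 (normal approximation).
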